9.5.3 PRO Analysis Population

The PRO analyses are based on the PRO Per Protocol Treated (PRO PPT) population, defined as all allocated participants who have PRO assessments available at both baseline and the specified postbaseline timepoint for the specific endpoint and have received at least one dose of the study intervention.

[figure not shown]

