Duration of Participation	
After a screening phase of up to 28 days, each eligible participant will be assigned to receive study intervention with pembrolizumab + lenvatinib (Arm 1, Cohorts A-G) or lenvatinib monotherapy (Arm 2, Cohort D only). Participants will continue on study intervention until disease progression is radiographically documented per RECIST 1.1 or RANO criteria for participants with GBM, unacceptable toxicity, withdrawal of consent, initiation of new anticancer treatment, intercurrent illness that prevents further administration of treatment, investigator's decision to discontinue the participant, pregnancy, administrative reasons requiring cessation of treatment or death. Pembrolizumab treatment will be discontinued once the participant has received 35 administrations of pembrolizumab (approximately 2 years). Participants in Arm 1 and Arm 2 may continue treatment with lenvatinib beyond 2 years if they experience clinical benefit according to the PI, with Sponsor consultation. In addition, discontinuation of study treatment with pembrolizumab and lenvatinib may be considered for participants who have attained a confirmed CR per RECIST 1.1 (or per RANO for GBM cohort) and have been treated for at least 24 weeks, receiving at least 2 additional doses of pembrolizumab beyond the date when the initial CR is declared.
 
Participants will be permitted to continue treatment beyond RECIST 1.1- or RANO-defined progression (Arm 1 only) as long as investigator-assessed clinical stability is observed, the participant is tolerating study intervention (Section 8.2.1.5 or Section 8.2.1.6) and after obtaining documented informed consent addendum. Treatment beyond confirmed progressive disease (PD) per iRECIST or RANO may be permitted on Sponsor consultation.
 
After the end of treatment (EOT), each participant will be followed for the occurrence of AEs and spontaneously reported pregnancy as described under Section 8.4.
 
Participants who discontinue study intervention without documented disease progression will have posttreatment follow-up imaging for disease status until the start of a new anticancer treatment, disease progression, pregnancy, death, withdrawal of consent, or the end of the study, whichever occurs first.
 
All participants will be contacted (by telephone or visit) approximately every 12 weeks to assess for survival status until death, withdrawal of consent, or the end of the study, whichever occurs first (unless this information is not allowed to be provided due to confidentiality).
 
The end of the study will be the date when the last participant completes the last study-related telephone call or visit, withdraws from the study, is lost to follow-up (ie, the participant is unable to be contacted by the investigator), or is planned to be enrolled in an extension study.

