4 STUDY DESIGN

4.1 Overall Design

This is a multicenter, open-label, Phase 2 study to evaluate the efficacy and safety of lenvatinib 20 mg qd in combination with pembrolizumab (Arm 1) in previously treated participants with TNBC (Cohort A), ovarian cancer (Cohort B), gastric cancer (Cohort C), CRC (Cohort D), GBM (Cohort E), BTC (Cohort F), or pancreatic cancer (Cohort G). The efficacy and safety of lenvatinib monotherapy (24 mg qd, Arm 2) will be evaluated in participants with CRC (Cohort D).

Initially, approximately 180 eligible participants will be stratified by tumor cohort (Cohorts A-F; 30 participants per cohort) and enrolled to receive lenvatinib 20 mg orally qd plus pembrolizumab 200 mg (IV q3w) for up to 35 administrations or until disease progression per RECIST 1.1 or RANO for the GBM cohort, unacceptable toxicity, withdrawal of consent, initiation of new anticancer treatment, intercurrent illness that prevents further administration of treatment, investigator's decision to discontinue the participant, pregnancy, administrative reasons requiring cessation of treatment, or death. Pembrolizumab treatment will be discontinued once the participant has received 35 administrations (approximately 2 years). Participants in Arm 1 and Arm 2 may continue

treatment with lenvatinib beyond 2 years if they experience clinical benefit according to the PI, with Sponsor consultation. Participants may discontinue treatment with pembrolizumab and lenvatinib if a CR has been attained per RECIST 1.1 (RANO for the GBM cohort) and they have been treated for at least 24 weeks, receiving at least 2 doses of pembrolizumab beyond the date when the initial CR was declared.

Potential for cohort expansion will be assessed for Cohorts A-F as described in Section 4.1.1. Additionally, 100 eligible participants with pancreatic cancer (Cohort G) will be enrolled to receive lenvatinib 20 mg orally qd plus pembrolizumab 200 mg (IV q3w) as described above. Enrollment into Cohort G will proceed as described in Section 4.1.2.

Participants will be permitted to continue treatment beyond RECIST 1.1- or RANO-defined progression (Arm 1 only) as long as investigator-assessed clinical stability is observed, the participant is tolerating study intervention (Section 8.2.1.5 or Section 8.2.1.6) and after obtaining documented informed consent addendum. Treatment beyond confirmed PD per iRECIST or RANO may be permitted on Sponsor consultation.

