4.2.3.3 Patient-reported Outcomes

Symptomatic improvement is considered a clinical benefit and accepted by health authorities. As part of the analyses for this study, participants will provide information regarding their health-related quality of life (HRQoL) via the following assessment tools: European Organization for the Research and Treatment of Cancer (EORTC) Quality of Life Questionnaire-Core 30 (QLQ-C30) and European Quality of Life 5-dimension 5-level (EQ-5D-5L) questionnaires. In addition, the following cohort-specific assessments tools will be used: QLQ-BR23 (Breast), QLQ-OV28 (Ovarian), QLQ-STO22 (Gastric), QLQ-CR29 (Colorectal), QLQ-BN20 (GBM), QLQ-BIL21 (Biliary), and QLQ-PAN26 (Pancreatic).

The PROs will be administered in the order below:

- EORTC- QLQ-C30
- EORTC- QLQ- disease-specific
- EQ-5D-5L

These measures are not pure efficacy or safety endpoints because they are affected by both disease progression and treatment tolerability.

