Completion of pembrolizumab q3w consists of 35 treatments (approximately 2 years). Note: participants experiencing a clinical benefit, according to the PI, may continue on lenvatinib beyond this time point with Sponsor consultation. Discontinuation of treatment may be considered for participants who have attained a confirmed CR and have been treated for at least 8 cycles (at least 24 weeks), receiving 2 cycles of the combination including 2 doses of pembrolizumab and at least 80% of the planned doses of lenvatinib beyond the date when the initial CR was declared.

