8.2.1.2 Tumor Imaging During the Study

The first on-study imaging assessment for all cohorts (except GBM) should be performed at 9 weeks (63 days \pm 7 days) from the date of treatment initiation. Subsequent tumor imaging should be performed every 9 weeks (63 days \pm 7 days) or more frequently if clinically indicated. After 54 weeks (378 days \pm 7 days), participants who remain on treatment will have imaging performed every 12 weeks (84 days \pm 7 days) or sooner if clinically indicated until Week 102. After Week 102, imaging should be performed q24w, or sooner if clinically indicated.

For participants with GBM, the first on-study imaging assessment should be performed at 6 weeks (42 days to 49 days) from the date of treatment initiation. Subsequent tumor imaging should be performed every 6 weeks (42 days \pm 7 days) until Week 18 and then every 9 weeks thereafter or more frequently if clinical indicated. After 54 weeks (378 days \pm 7 days), participants who remain on treatment will have imaging performed every 12 weeks (84 days \pm 7 days) or sooner if clinically indicated until Week 102. After Week 102, imaging should be performed q24w, or sooner if clinically indicated.

Imaging timing should follow calendar days from treatment initiation and should not be adjusted for delays in cycle starts. Imaging should continue to be performed until disease progression is identified by the investigator (unless the investigator elects to continue treatment and follow iRECIST), the start of new anticancer treatment, withdrawal of consent, death, or notification by the Sponsor, whichever occurs first. All supplemental imaging must be submitted to the iCRO.

For participants with GBM, brain MRI is required at baseline and all time points for efficacy assessments. For non-GBM cohorts, participants with previously treated brain metastases are required to have a brain MRI at screening and at all subsequent tumor assessment time points. A brain MRI is also required for all participants when clinically indicated.

OR should be confirmed by a repeat imaging assessment. Tumor imaging to confirm PR or CR should be performed at least 4 weeks after the first indication of a response is observed. Participants will then return to regular scheduled imaging, starting with the next scheduled imaging time point. Participants who receive additional imaging for confirmation do not need to undergo the next scheduled tumor imaging if it is less than 4 weeks later; tumor imaging

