8.2.2 Patient-reported Outcomes

Health-related QoL will be assessed at Cycle 1 Day 1 (before the first dose of study intervention), every cycle through Cycle 13, Cycle 17, Cycle 21, at the time of discontinuation (EOT Visit), and the 30-day Safety Follow-up Visit (See SoA in Section 1.3 for electronic patient-reported outcomes [ePRO] administration schedule). If the EOT Visit occurs 30 days from the last dose of study treatment, a Safety Follow-up Visit is not required, ePROs do not need to be repeated.

HRQoL questionnaires will be administered by trained site personnel and completed electronically by participants in the following order: EORTC QLQ-C30 first, then the cohort-specific ePROs listed below, and EuroQoL EQ-5D last:

- Breast (QLQ-BR23)
- Ovarian (QLQ-OV28)
- Gastric (QLQ-STO22)
- Colorectal (QLQ-CR29)
- GBM (QLQ-BN20)
- Biliary (QLQ-BIL21)
- Pancreatic (QLQ-PAN26)

It is best practice and strongly recommended that electronic patient-reported outcomes (ePROs) are administered to allocated participants prior to drug administration, AE

evaluation, and disease status notification. If the participant does not complete the ePROs at a scheduled time point, the MISS_MODE form must be completed to capture the reason the assessment was not performed.

If at the time of enrollment of a participant, the translated version of any PRO measure is not available for that language/country, and therefore cannot be completed by the participant at Cycle 1 Day 1, then the PRO measure will not be required for this participant at any point during the study. The other study PRO measures must be completed as scheduled.

NOTE: For some sites, the translated PRO measure might become available after study startup and should be administered to participants at their time of enrollment; for some sites, the PRO measure translation might not be available for the entire duration of the study.

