8.10.4.2 Efficacy Follow-up Visits

Participants who complete the protocol-required cycles of study intervention or who discontinue study intervention for a reason other than disease progression will move into the Efficacy Follow-up Phase and should be assessed according to the same imaging schedule used while on treatment. Calculated from the date of first dose, imaging should be performed every 9 weeks (63 days ± 7 days), or more frequently if clinically indicated. After 54 weeks (378 days ± 7 days), participants will have imaging performed every 12 weeks (84 days ± 7 days) or sooner if clinically indicated until Week 102. After Week 102, imaging should be performed every 24 weeks, or sooner if clinically indicated, to monitor disease status. For participants with GBM, imaging to be performed at 6 weeks (42 days to 49 days) from the date of treatment initiation. Subsequent tumor imaging should be performed every 6 weeks (42 days ± 7 days) until Week 18 and then every 9 weeks thereafter or more frequently if clinical indicated. After 54 weeks (378 days ± 7 days), participants who remain on treatment will have imaging performed every 12 weeks (84 days ± 7 days) or sooner if clinically indicated until Week 102. After Week 102, imaging should be performed q24w, or sooner if clinically indicated. Imaging timing should follow calendar days from treatment initiation. Participants who completed all efficacy assessments and/or will not have further efficacy assessments must enter the Survival Follow-up Phase.

If a clinic visit is not feasible, the participant may be contacted by telephone or email. Every effort should be made to collect information regarding disease status until the start of new anticancer therapy, disease progression, death, end of study. Information regarding poststudy anticancer treatment will be collected if new treatment is initiated. Participants will also be asked to complete HRQoL questionnaires as outlined in Section 8.2.2.

All participants who discontinue study intervention before disease progression will continue to undergo tumor assessments in the imaging follow-up phase until disease progression or a new anticancer therapy is initiated, unless the participant withdraws consent.

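### Section 9.5.3 limits the PRO analyses to participants with both a baseline and a specified later score, so the exploratory change-from-baseline results describe those still answering and plausibly understate worsening at later visits

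*Combined protocol and SAP*

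**What the plan says.** Section 9.5.3 defines the PRO population as "all allocated participants who have PRO assessments available at both baseline and the specified postbaseline timepoint for the specific endpoint", who have also had at least one dose. The readable text gives no other PRO population.

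Section 8.2.2 schedules the questionnaires at Cycle 1 Day 1 and then "every cycle through Cycle 13, Cycle 17, Cycle 21, at the time of discontinuation (EOT Visit), and the 30-day Safety Follow-up Visit". Section 3 places the PRO objective among the tertiary/exploratory ones and names two quantities: change from baseline, and time to deterioration (TTD) on the QLQ-C30 subscales. Section 9.4.3 says that data will be summarized at pre-specified time points and leaves time points, scoring and details to the supplemental SAP (sSAP).

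Two further statements bear on who goes on answering. Section 4.2.3.3 says of the PRO measures that "they are affected by both disease progression and treatment tolerability". The synopsis (1.1) says: "Participants will continue on study intervention until disease progression is radiographically documented per RECIST 1.1 or RANO criteria for participants with GBM, unacceptable toxicity", among other reasons for stopping.

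**The concern.** A treated participant with a baseline score but no score at the specified visit is outside the analysis at that visit. The events that worsen scores are also events that stop scores being collected. The remaining participants are then likely to be doing better than the treated group as a whole, and more so as follow-up lengthens. A change-from-baseline table could look more stable than the treated group was, and a reader could not tell without completion figures beside it.

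A second problem needs no assumption about missing data. TTD follows a participant to deterioration or censoring. Requiring a score at one specified later visit would exclude people who deteriorated and then stopped answering.

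The stakes are limited. The objective is exploratory and Sections 9.3 and 9.8 plan no hypothesis test, so no conclusion on objective response rate or safety depends on this.

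**Working it through.** The plan gives no PRO completion rate, standard deviation or target difference, so it has no figure to reproduce. The documents support a timing check. The size can only be illustrated.

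**1. Questionnaires at risk.** Inputs: 21-day cycles (1.3) and the schedule in 8.2.2. Cycles 1 to 13, 17 and 21 make 15 cycle assessments, 14 of them post-baseline. Cycle k Day 1 falls 21 × (k − 1) days after first dose: Cycle 3 on day 42, Cycle 4 on day 63, Cycle 5 on day 84, Cycle 6 on day 105.

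**2. First scheduled scan.** Section 8.2.1.2: "The first on-study imaging assessment for all cohorts (except GBM) should be performed at 9 weeks", that is day 63. For glioblastoma it is day 42. Section 8.2.2 strongly recommends completing questionnaires before participants hear their disease status, so the one due on the scan day should precede any effect of that scan.
- Non-glioblastoma: Cycles 5 to 13 (9) plus 17 and 21 = 11 of 14.
- Glioblastoma: Cycles 4 to 13 (10) plus 17 and 21 = 12 of 14.

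These are nominal counts. Visit windows and unscheduled scans are ignored.

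**3. Later start for stable Arm 1 participants.** Treatment beyond progression is allowed in Arm 1 only (4.1). Under 8.2.1.5, clinically stable participants should not be discontinued until progression is confirmed, with repeat imaging 4 to 8 weeks later. For a non-glioblastoma participant with first progression on day 63, confirmation comes at the earliest on day 63 + 28 = 91. The first questionnaire after that is Cycle 6 (day 105), so 8 + 2 = 10 of 14 remain exposed. Arm 1 is most of the trial: 30 + 30 + 100 + 100 + 100 + 100 + 100 = 560 of 590 planned participants. In the other direction, toxicity, clinical progression or death can remove a questionnaire before any scan.

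**4. An opposing force.** Section 7.1: "Discontinuation of treatment may be considered for participants who have attained a confirmed CR and have been treated for at least 8 cycles". Responders who stop would make those remaining look worse. This cannot act before Cycle 9, so it can touch Cycles 9 to 13, 17 and 21 (7 of 14) but not Cycles 2 to 8.

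**5. Size, illustration only.** Let p be the share answering and d the number of points by which the mean change of those not answering is worse. The full-set mean is p × (answering mean) + (1 − p) × (non-answering mean), so the answering mean exceeds it by (1 − p) × d. All inputs below are assumed, on an assumed 0–100 scale.

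| p | d | (1 − p) × d |
|---|---|---|
| any | 0 | 0 |
| 0.8 | 5 | 1.0 |
| 0.5 | 10 | 5.0 |
| 0.4 | 20 | 12.0 |
| 0.8 | −5 | −1.0 |
| 0.4 | −5 | −3.0 |

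The range includes zero and both signs, and nothing in the documents narrows it.

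**The case against.** The strongest reply is that the plan cannot be judged on this from what is visible. Section 9.4.3 defers details to the sSAP, 7.3 refers to pre-specified missing-data guidelines, and part of 9.6 is blacked out. That stands against one tempting inference, that no missing-data method is planned: the documents do not support it. It does not remove the visible entry rule, which restricts who reaches whatever model follows.

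Next, any observed change needs both scores, so the rule is partly a matter of definition. That is fair for a simple descriptive table. It does not justify making the same set the basis of the PRO analyses generally, TTD included. The contrast with 9.4.1, where missing response counts as nonresponse, carries little weight, because a binary rule has no direct counterpart for a continuous score.

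Other stronger readings also fail:
- **Counting the scan-day questionnaire as exposed** would give 12 of 14 (13 of 14 for glioblastoma). The order recommended in 8.2.2 argues against that.
- **Calling the understatement certain, or giving it a number.** Some missingness is unrelated to health, such as an unavailable translation (8.2.2), and stopping after complete response works the other way.
- **Reading 8.10.4.2 as contradicting 8.2.2.** It says "Participants will also be asked to complete HRQoL questionnaires as outlined in Section 8.2.2", so it defers to 8.2.2, which schedules nothing after the 30-day visit.

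End-of-treatment and 30-day scores will capture some worsening in those who stop. The visible text does not say how, or whether, they are mapped to cycle visits.

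**Conclusion.** The point holds in a limited form. As written, 9.5.3 yields a completers' summary, and the protocol's own statements make understated worsening plausible at later visits. By nominal schedule, 11 of 14 post-baseline cycle questionnaires (12 of 14 for glioblastoma) follow the first scheduled scan, with a later start for stable Arm 1 participants treated until progression is confirmed. The size is unknown and may be zero. The direction rests on the assumption that those who stop answering fare worse on average. The misfit with TTD rests on the wording alone. Only exploratory PRO results are touched. This is a cheap improvement that the sponsor could make, not a defect that threatens the trial's conclusions.

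**What to change.** Change 9.5.3, with the detail in the sSAP:

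- **Population:** all participants with at least one dose of study intervention and at least one PRO assessment for the instrument.
- **Change from baseline:** for the main scores (for example QLQ-C30 global health status), a constrained longitudinal or mixed model on all available scores at a few pre-specified visits. State the missing-at-random assumption and how end-of-treatment and 30-day scores are mapped.
- **Covariance:** keep it simple in the groups of about 30 (Cohorts A and B, Cohort D Arm 2). An unstructured matrix has k(k + 1)/2 parameters: 120 for all 15 cycle assessments, 15 for baseline plus four visits. Compound symmetry has 2.
- **TTD:** do not require a score at a specified later visit.
- **Completion:** number and percent at each visit, with the MISS_MODE reasons.
- **Current set:** keep as a supportive table labelled completers only.
- **Optional:** a delta-adjusted sensitivity analysis.

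If the sSAP already does this, align 9.5.3 with it. Section 9 allows analysis changes outside the primary and key objectives to be documented in the sSAP before final database lock.

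No new data are needed, since reasons for missed questionnaires are already collected. Limiting the models to main scores keeps the work modest: the QLQ-C30 alone has 5 + 3 + 6 + 1 = 15 scores, and 15 × 8 cohort-arm groups would be 120 models. The downside is reliance on missing at random, which may remove only part of any bias.

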9.6 Statistical Methods

Both efficacy and safety analyses will be assessed by arm within each cohort.

[figure not shown]
CCI

CCI

CCI

9.6.2 Statistical Methods for Safety Analyses

Safety and tolerability will be assessed by clinical review of all relevant parameters including AEs, laboratory tests, vital signs, and ECG measurements. All safety analyses will be performed in the APaT population by treatment arm within each cohort.

Adverse Events

Events will be summarized based on number and proportion of total participants by system organ class and preferred term. Separate summaries with descriptive statistics (counts and percentage) will be given for all AEs, treatment-related AEs, AEs by toxicity grade, SAEs and AEs leading to discontinuation of study intervention and dose modification.

ECIs will be identified and additional summaries provided.

[figure not shown]
The incidence of deaths and the primary cause of death will be summarized.

Further details on the statistical approach of safety analysis will be described in the sSAP.

[figure not shown]
